3	Impaired liver function, defined as alanine aminotransferase (ALAT) \geq = 2.5 times upper limit of normal (one retest analysed at the central laboratory within a week is permitted with the result of the last sample being conclusive).	Cirrhosis. ICD-9 Diagnosis: 571.2, 571.5, 571.6 ICD-10 Diagnosis: K70.11, K70.2, K70.3x, K70.4x, K74.x Hepatic decompensation:	
		ICD-9 Diagnosis: 456.0, 456.20, 456.1, 456.21, 789.5, 789.59, 572.2, 567.0, 567.2, 567.21, 567.22, 567.29, 567.8, 567.89, 567.9, 572.4 ICD-10 Diagnosis: R18.x, 185.x, K72.x, K65.x, K66.x, K67 HCC is already excluded with exclusion criterion 9	
		Measured 180 days prior to and including the day of drug initiation in any diagnosis position and inpatient or outpatient care setting:	
4	Subjects known to be Hepatitis B antigen or Hepatitis C antibody positive.	Viral hepatitis B or C: ICD-9 diagnosis: 070.2x, 070.3x, 070.4x, 070.51, 070.54, 070.71, 070.74, V02.61, V02.62 ICD-10 diagnosis: B16.x, B17.0, B17.1x, B18.0-B18.2, B19.1x, B19.2x, Z22.51, Z22.52	
		Measured 180 days prior to and including the day of drug initiation in any diagnosis position and inpatient or outpatient care setting:	
5	Impaired renal function defined as serum creatinine $>= 135 \mu moVL$ ($>= 1.5 mg/dL$) for males and $>= 110 \mu moVL$ ($>= 1.3 mg/dL$) for females (one retest analysed at the central laboratory within a week is permitted with the result of the last sample being conclusive)	CKD stage 5. End-stage renal disease, dialysis or renal transplant; ICD-9 diagnosis: 585.5, 585.6, 996.81, V42.0, V45.1x, V56.xx ICD-9 procedure: 39,95, 54.98, 55.6x ICD-10 diagnosis: N18.5, N18.6, R88.0, T82.41, T82.42, T82.49, T85.611, T85.621, T85.631, T86.1x, Y84.1, Z48.22, Z49.xx, Z91.15, Z94.0, Z99.2 ICD-10 procedure: 0TY00Zx, 0TY10Zx, 3E1M39Z, 5A1Dx0Z CPT: 50360, 50365, 90920, 90921, 90924, 90925, 90935, 90937, 90939, 90940, 90945, 90947, 90957, 90958, 90959, 90960, 90961, 90962, 90965, 90966, 90969, 90970, 90989, 90993, 90999, 9097, 99512, 99559, 99512, G0257, G0314, G0315, G0314, G0315, G0316, G0317, G0318, G0319, G0327, G0333, G0326, G0327, S0333, S0330, S	
		Measured 180 days prior to and including the day of drug initiation in inpatient care setting, any position:	
6	Clinically significant active cardiovascular disease including history of myocardial infarction within the past 6 months and/or heart failure (New York Heart Association class III and IV) at the discretion of the investigator.	Myocardial Infarction: ICD-9 DX: 410.xx ICD-10 DX: 110.xx, 122.xx ICD-10 DX: 121.xx, 122.xx Measured 180 days prior to and including the day of drug initiation in inpatient care setting, primary position: Heart Failure: ICD-9 DX: 428.xx, 398.91, 402.x1, 404.x1, 404.x3 ICD-10 DX: 109.81, 111.0, 113.0, 113.2, 150.xxx, 197.13x	
		NB. HF is included only if inpatient / primary position to detect the most severe cases as specified in the exclusion criterion of the trial	

			1
		Measured 180 days prior to and including the day of drug initiation:	
		Anti-VEGFi CPT: 67028 (Intravitreal injection for pharmacologic agent)	
		AND	
7	Proliferative retinopathy or maculopathy requiring acute treatment as judged by the investigator.	HCPCS: J9035 OR C9257 OR Q5107 (Bevacizumab 10 mg injection) OR HCPCS: J2778 (Ranibizumab 0.1 mg) OR HCPCS: C9291 OR Q2046 OR J0178 OR C9296 OR J9400 (Aflibercept 2 mg injection)	
		Photocoagulation: CPT: 67228 (Panretinal photocoagulation) OR CPT: 67220 (Focal/Grid photocoagulation) OR CPT: 67028 (Intravitreal injection for pharmacologic agent)	
		Measured 180 days prior to and including the day of drug initiation in any diagnosis position in the inpatient and outpatient and emergency care setting:	
		Hypertensive crisis ICD-10 diagnosis: $116.x$ (includes hypertensive urgency, emergency, crisis, unspecified)	
		OR	
8	Uncontrolled treated/untreated hypertension (systolic blood pressure ≥= 180 mmHg and/or diastolic blood pressure ≥= 100 mmHg).	Measured 180 days prior to and including the day of drug initiation in primary diagnosis position for inpatient or any position for emergency care setting:	
	blood pressure >= 100 mmng).	Uncontrolled hypertension: ICD-9 diagnosis:	
		401.9 (unspecified essential hypertension) 401.0 (malignant essential hypertension)	
		402.0x (malignant hypertensive heart disease) 403.0x (malignant hypertensive kidney disease)	
		404.0x (malignant hypertensive heart and kidney disease) 405.0x (malignant secondary hypertension)	
		403.9x (unspecified hypertensive kidney disease) 796.2 (elevated BP reading without Dx of HTN)	
	Cancer (except basal cell skin cancer or squamous cell skin cancer) or any clinically significant	Measured 1825 prior to and including the day of drug initiation in any diagnosis position and inpatient or outpatient care setting:	
9	Cancer (except basis cension cancer of squamous cension cancer) of any clinically significant disease or disorder, except for conditions associated to type 2 diabetes, which in the investigator's opinion could interfere with the results of the trial.	Cancer:	
	arrowgant of opinion could metrore with the regard of the filler.	ICD 9 diagnosis: 140.x-209.x (except 173.x, non-melanoma skin cancer and 209.4x, 209.5x, 209.6x) ICD 10 diagnosis: C00.x-C96, D45 (except C44.x, non-melanoma skin cancer)	
		At least two measurements in the 180 days prior to and including the day of drug initiation inpatient or emergency department settings:	
10	Recurrent major hypoglycaemia as judged by the investigator.	Hypoglycemia: ICD-9 diagnosis: 251.0, 251.1, 251.2, 962.3, or 270.3 (primary position) or 250.8 without co-existence of 259.8, 272.7,	
		681.x,682.x, 686.9, 707.1–707.9, 730.0–730.2, or 731.8 (any position) ICD-10 diagnosis: E10.641, E11.641, E13.641, E10.649, E11.649, E13.649, E16.0, E16.1, E16.2 (primary position) or E11.69, E13.69, E10.69 without coexistence of E34.1, E34.8, E35, E75.2, E75.3, E77, L01, L02, L03, L97, M86, M90	
N/A	Known or suspected allergy to trial product(s) or related products.	N/A	
		Measured 90 days prior to and including the day of drug initiation:	
		Injectable (IV) or (IM);	
11	Use of any drug (except for OADs), which in the investigator's opinion could interfere with glucose levels (e.g. systemic corticosteroids).	NDC Generic Name: methylprednisolone, hydrocortisone, dexamethasone CPT/HCPCS Procedure Code: J1020, J1030, J1040, J1720, J2920, J2930	
		Oral:	
		NDC Generic Name: Cortisone, hydrocortisone, prednisone, prednisolone, methylprednisolone, dexamethasone	
N/A	Receipt of any investigational drug within the four weeks prior to this trial.	N/A	
N/A	Previous participation in the randomised phase of this trial. Re-screening is allowed once within the recruitment period.	N/A	
14/24	·		

		Manual 180 days single and including the day of days intrinsic in any dispersion of the contract of the contra	1
		Measured 180 days prior to and including the day of drug initiation in any diagnosis position in inpatient or outpatient care setting:	

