5.3 Flowchart of the study cohort assembly

For liraglutide vs. glimepiride: Aetion link: https://bwh-dope.aetion.com/cohorts/details/23482/1688/71700

	Optum	
	Excluded Patients	Remaining Patients
All patients		79,335,559
Did not meet cohort entry criteria	-78,554,666 (99%)	780,893
Excluded due to insufficient enrollment	-119,528 (15%)	661,365
Excluded due to prior use of referent	-424,186 (64%)	237,179
Excluded due to prior use of exposure	-138,679 (58%)	98,500
Excluded because patient qualified in >1 exposure category	-85 (<1%)	98,415
Excluded based on nursing home admission in the prior 180 days	-3,784 (4%)	94,631
Excluded based on gender missing or unknown	-10 (<1%)	94,621
Excluded based on Inclusion #1.1 - Type 2 diabetes mellitus	-6,027 (6%)	88,594
Excluded based on Inclusion #1.2 - Metformin use (2 prescriptions within 183 days)	-55,832 (63%)	32,762
Excluded based on Inclusion #1.3 - Concomitant initiation or concurrent use of metformin	-3,670 (11%)	29,092
Excluded based on Inclusion #1.4 - No use of other anti-diabetic meds	-9,861 (34%)	19,231
Excluded based on Inclusion #2.1 - 3 records of HbA1c 2-20% values/results within 365 days	-13,962 (73%)	5,269
Excluded based on Inclusion #2.2 - At least 1 lab value HbA1c 7-11% recorded within 90 days	-808 (15%)	4,461
Excluded based on Inclusion #3.1 - Age > 18	-0 (<1%)	4,461
Excluded based on Inclusion #3.2 - Age < 80	-87 (2%)	4,374
Excluded based on Exclusion #1 - Morbid Obesity BMI > 40	-147 (3%)	4,227
Excluded based on Exclusion #2 - Any insulin use	-234 (6%)	3,993
Excluded based on Exclusion #3 - End-stage liver disease	-9 (<1%)	3,984
Excluded based on Exclusion #4 - Viral Hepatitis B and C	-7 (<1%)	3,977
Excluded based on Exclusion #5 - CKD stage 5, End-stage renal disease, dialysis, or renal transplant	-0 (<1%)	3,977

Excluded based on Exclusion #6.1 - Myocardial Infarction	-1 (<1%)	3,976
Excluded based on Exclusion #6.2 - Heart Failure	-1 (<1%)	3,975
Excluded based on Exclusion #7 - Anti-VEGFi OR Photocoagulation	-5 (<1%)	3,970
Excluded based on Exclusion #8 - Uncontrolled hypertension	-34 (<1%)	3,936
Excluded based on Exclusion #9 - Malignant neoplasm (except non-melanoma skin cancer)	-79 (2%)	3,857
Excluded based on Exclusion #10 - Recurrent Hypoglycemia	-8 (<1%)	3,849
Excluded based on Exclusion #11 - Systemic glucocorticoids use	-48 (1%)	3,801
Excluded based on Exclusion #12 - Drug addiction or alcohol abuse and dependence	-11 (<1%)	3,790

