6.3.1 Outcome variables

Effectiveness outcome variables of interest (definitions provided in **Appendix A**):

• **Primary outcome:** Changes in HbA1c from baseline to 26 weeks of treatment (end of follow-up).

Note. In the trial, HbA1c was also measured at 8, 12, 18 weeks (± 3 days) after randomization. Missing values of HbA1c at 26 weeks were replaced using last observation carried forward (LOCF) in the intention-to-treat (ITT) analysis set. In the replication, HbA1c at baseline will be defined as the last recorded HbA1c value measured within 90 days before and including cohort entry date in both groups. HbA1c at the end of follow-up will be defined as a recorded HbA1c value closest to the end of the 26th week and measured between 56 and 212 days (8-30 weeks) after cohort entry.

Secondary outcome: --

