6.3.2 Primary analysis and study follow-up

As-treated (AT) analysis will be performed as main analysis. The treatment drug will be defined as the index drug assigned on the day of cohort entry. Patients will be followed for about 30 weeks (212 days). Compared to the trial (Nauck M et al. 2009), we will

extend the follow-up and the outcome assessment periods of 4 weeks. The follow-up and outcome assessment window will start 56 days after cohort entry date and will continue until the earliest date of the following events:

- The first occurrence of the outcome of interest (measured between 56 and 212 days after cohort entry),
- The date of end of continuous registration in the database (disenrollment or end of available data),
- End of the study period,
- Measured death event occurs,
- Index drugs discontinuation (liraglutide, glimepiride or metformin),
- Crossover or addition of drug from the other treatment group,
- Addition of any other anti-diabetic medications,
- Nursing home admission
 - Nursing home admissions are considered a censoring event because the data sources utilized typically provide little to no data on a patient, particularly on drug utilization, after admission. We will utilize this as an exclusion reason for cohorts for the same reason.

Note. To decrease the incidence of missing values of the outcome (specifically, missing of HbA1c values measured between 56-212 days after cohort entry), we required that the eligible patients had at least 3 HbA1c measurements recorded within 365 days before and including cohort entry. This will increase the probability of including in the final cohort patients who are adherent to a routinely HbA1c testing and, consequently, will decrease the frequency of missing values of the outcome. Multiple imputation will be used to handle missing values in the primary analysis, while complete case analysis will be applied in a sensitivity analysis.

7. Initial Feasibility Analysis

Aetion report name:

For liraglutide vs. glimepiride

Optum CDM (continuous HbA1c outcome) https://bwh-dope.aetion.com/projects/details/1688/rwrs/71723

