2	HbA1c: -7.0-10.0% (both incl.) in subjects on OAD combination therapy -7.0-11.0% (both incl.) in subjects on OAD monotherapy.	2.1 Selecting patients with 3 measurements of HbA1c values (between 2-20%) recorded within 365 days prior to and including cohort entry: Loine codes: 17855-8, 17856-6, 41995-2, 43150-2, 4548-4, 4549-2, 55454-3, 71875-9, 74246-0 AND Result value 2-20% 2.2 Selecting patients with at least one measurement of HbA1c value (between and included 7-11%) recorded within the last 91 days prior to and including cohort entry: Loine codes: 17855-8, 17856-6, 41995-2, 43150-2, 4548-4, 4549-2, 55454-3, 71875-9, 74246-0 AND Result value 7-11%		
3	Age 18-80 years, both inclusive (as allowed according to local guidelines for metformin and glimepiride treatment). This inclusion criterion has been modified for Site 344 in Australia according to Substantial Protocol Amendment No. 1-AU, see Section 9.8.1.	Female and male, 18-80 years at the time of drug initiation		
	EXCLU]	

		Measured 180 days prior to and including the day of drug initiation inpatient (any position), outpatient (any position):	
1	Body mass index (BMI) >= 40.0 kg/m2.	Morbid obesity diagnosis or BMI >= 40 kg/m2: ICD 9 diagnosis: 278.01, 278.03, V85.4x ICD 10 diagnosis: E66.01, E66.2, Z68.4x	
		NB. Codes for bariatric surgey, complications of bariatric surgery and prescriptions of drugs for weight loss were not included in the measure since this exclusion criterion aims to exclude specifically patients with morbid obesity. Codes for obesity during pregnancy were not included because of the exclusion criterion #17.	
		Measured 180 days prior to and including the day of drug initiation:	
		NDC Generic Name:	
2	Treatment with insulin within the last three months prior to trial (except for short-term treatment due to intercurrent illness at the discretion of the investigator).	Please refer to Insulin in "Anti-diabetic treatments"	
		NB. Although the trial excluded patients in treatment with insulin within the 90 days before drug initiation, with real- world data we are required to be more conservative and to extend the washout period to 180 days. In fact, a 90-day washout applied in real world does not garantee the exclusion of prevalent users (i.e. patients on active insulin therapy) from the cohort.	
		Measured 180 days prior to and including the day of drug initiation in any diagnosis position and inpatient or outpatient care setting:	

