Appendix B

Appendix B

-		UNMATCHED	
		Optum	
Variable Number of patients	Glimpiride 3,096	Liraglutide 378	St. Diff
Age squared			
mean (sd) ge (continuous)	761406 (223830.2)	651214 (225218.8)	0.491
mean (sd) te (categories)	64.24 (10.37)	59.22 (10.94)	0.471
8 - 40; n (%)	95 (3.1%)	20 (5.3%)	-0.110
1 -50; n (%) 1 -60; n (%)	266 (8.6%) 602 (19.4%)	64 (16.9%) 106 (28.0%)	-0.251 -0.203
- 70; n (%) - 80; n (%)	1187 (38.3%)	133 (35.2%) 55 (14.6%)	0.064 0.390
ler	946 (30.6%)		
: MALE; n (%) FEMALE; n (%)	1726 (55.7%) 1370 (44.3%)	179 (47.4%) 199 (52.6%)	0.167 -0.167
ite; n (%) white; n (%)	1492 (48.2%) 1604 (51.8%)	220 (58.2%) 158 (41.8%)	-0.201 0.201
ndar time years (Jan 2010 - Jun 2020)			
n 26, 2010 - Dec 31, 2017; n (%) n 1, 2018 - Jun 30, 2020; n (%)	1850 (59.8%) 1246 (40.2%)	255 (67.5%) 123 (32.5%)	-0.161 0.161
al Health			
ng; n (%) y or Overweight; n (%)	296 (9.6%) 760 (24.5%)	30 (7.9%) 93 (24.6%)	0.060 -0.002
ty; n (%) reight: n (%)	554 (17.9%) 247 (8.0%)	79 (20.9%) 16 (4.2%)	-0.076 0.159
ned comorbidity score, 180 days			
(sd) core: Empirical Version 180 days	2.06 (1.56)	1.86 (1.36)	0.137
(sd)	0.99 (0.77)	1.03 (0.73)	-0.053
bA1c	8.16 (0.96)	8.18 (0.99)	-0.021
sd) scular Comorbidities			
sion; n (%) demia; n (%)	391 (12.6%) 2296 (74.2%)	66 (17.5%) 299 (79.1%)	-0.137 -0.116
erosis Disease (MI, angina, CAD and other forms of chronic ischemic	566 (18.3%)	43 (11.4%)	0.116
ease, History of CABG or PTCA); n (%) : n (%)	64 (2.1%)	3 (0.8%)	0.195
vII; n (%)	10 (0.3%)	1 (0.3%)	0.000
nstable angina; n (%) angina; n (%)	18 (0.6%) 80 (2.6%)	1 (0.3%) 6 (1.6%)	0.045 0.070
other forms of chronic ischemic heart disease; n (%)	415 (13.4%)	30 (7.9%)	0.179
y of CABG or PTCA; n (%)	107 (3.5%)	9 (2.4%)	0.065
r PAD surgery; n (%) vascular disease (Stroke, TIA, Late effects); n (%)	166 (5.4%) 77 (2.5%)	11 (2.9%) 2 (0.5%)	0.126 0.165
e (Ischemic or hemorrhagic); n (%)	40 (1.3%)	1 (0.3%)	0.112
n (%) effects of cerebrovascular disease; n (%)	27 (0.9%) 28 (0.9%)	1 (0.3%) 0 (0.0%)	0.078 0.135
ailure; n (%) brillation: n (%)	103 (3.3%)	10 (2.6%)	0.041
illation; n (%) diac dysrhythmia; n (%)	121 (3.9%) 190 (6.1%)	14 (3.7%) 18 (4.8%)	0.010 0.057
s Mellitus Comorbidities			
remia; n (%) nephropathy; n (%)	20 (0.6%) 434 (14.0%)	4 (1.1%) 48 (12.7%)	-0.054 0.038
Neuropathy; n (%)	495 (16.0%)	60 (15.9%)	0.003
: Retinopathy; n (%) is with unspecified complications; n (%)	134 (4.3%) 122 (3.9%)	20 (5.3%) 14 (3.7%)	-0.047 0.010

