es with peripheral circulatory disorders and amputations, DF; n (%)*	70 (2.3%)	9 (2.4%)	-0.007
etes with peripheral circulatory disorders; n (%) er-limb amputations; n (%)	38 (1.2%) 4 (0.1%)	5 (1.3%) 1 (0.3%)	-0.009 -0.045
tic Foot; n (%)	32 (1.0%)	3 (0.8%)	0.021
omorbidities : kidney disease stages I-IV and NOS; n (%)	381 (12.3%)	40 (10.6%)	0.053
laneous renal disease; n (%)	109 (3.5%)	10 (2.6%)	0.052
disorders (Anxiety and Depression); n (%) ety; n (%)	332 (10.7%) 211 (6.8%)	47 (12.4%) 27 (7.1%)	-0.053 -0.012
sion; n (%)	162 (5.2%)	28 (7.4%)	-0.091
morbidities ive sleep apnea; n (%)	259 (8.4%)	41 (10.8%)	-0.082
%)	207 (6.7%)	9 (2.4%)	0.207
n (%) hrosis: n (%)	96 (3.1%) 363 (11.7%)	14 (3.7%) 49 (13.0%)	-0.033 -0.040
FLD; n (%)	98 (3.2%)	16 (4.2%)	-0.053
ons	2585 (83.5%)	324 (85.7%)	-0.061
rtensive medications; n (%) RBs; n (%)	2257 (72.9%)	285 (75.4%)	-0.061
ckers; n (%) channel blockers; n (%)	971 (31.4%) 795 (25.7%)	94 (24.9%) 83 (22.0%)	0.145 0.087
channel blockers; n (%) : n (%)	369 (11.9%)	52 (13.8%)	-0.057
cs; n (%)	1108 (35.8%)	133 (35.2%)	0.013
ther lipid-lowering drugs; n (%) : n (%)	2402 (77.6%) 2285 (73.8%)	291 (77.0%) 273 (72.2%)	0.014 0.036
(%)	370 (12.0%)	49 (13.0%)	-0.030
zing Medications; n (%)	507 (16.4%) 719 (23.2%)	72 (19.0%) 129 (34.1%)	-0.068 -0.243
ts; n (%)	540 (17.4%)	105 (27.8%)	-0.251
/hypnotics; n (%) pine; n (%)	114 (3.7%) 256 (8.3%)	25 (6.6%) 42 (11.1%)	-0.131 -0.095
ids; n (%)	319 (10.3%)	49 (13.0%)	-0.084
lization dication claims			
1)	11.47 (6.60)	12.82 (6.94)	-0.199
of office visits sd)	4.76 (3.58)	5.24 (3.72)	-0.131
hospitalizations or ED visits			
) Endocrinologist visits	0.24 (0.87)	0.20 (0.66)	0.052
sd)	0.13 (0.55)	0.27 (0.85)	-0.196
of HbA1c test orders sd)	1.77 (0.68)	1.79 (0.78)	-0.012
l) lexible Sigmoidoscopy or colonoscopy or CT virtual colonoscopy (CRC	1.77 (0.68)	1.79 (0.78)	-0.012
ng); n (%)		,,	
	400 (12.9%) 120 (3.9%)	59 (15.6%) 16 (4.2%)	-0.077 -0.015
	659 (21.3%)	93 (24.6%)	-0.079
r of Pap smear (Cervical cancer screening); n (%) cine; n (%)	671 (21.7%)	82 (21.7%)	0.000
of Pap smear (Cervical cancer screening); n (%) ine; n (%) scoccal vaccine; n (%)		0.03 (0.18)	0.002
r of Paps smear (Cervical cancer screening); n (%) icine; n (%) scoccal vaccine; n (%) or DDAR tests (sd)	0.04 (0.19)	0.03 (0.18)	
of Paps mear (Cervical cancer screening); n (%) ine; n (%) occacial vaccine; n (%) of DXA tests (sd) or pharmacy cost (charges in U.S. \$)			-D 331

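### Eligibility guarantees at least three pre-entry HbA1c results, but the visible adjustment set uses only the last level; add the earlier mean as one covariate and name it in the imputation model

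*Combined protocol and SAP*

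**What the plan says.** The Note in section 6.3.2 requires that "eligible patients had at least 3 HbA1c measurements recorded within 365 days before and including cohort entry". It opens with the reason: "To decrease the incidence of missing values of the outcome". No other use of these results is stated. Appendix A, inclusion 2.1, repeats the rule for values between 2% and 20%, with no minimum spacing and no requirement that the dates differ.

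Section 6.3.1 fixes the baseline: "HbA1c at baseline will be defined as the last recorded HbA1c value measured within 90 days before and including cohort entry date".

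Appendix B shows one HbA1c level before matching, 8.16 (SD 0.96) for glimepiride against 8.18 (0.99) for liraglutide, standardised difference -0.021. It also shows the number of HbA1c test orders, 1.77 against 1.79. No earlier level, mean or slope is visible. In the copy reviewed the table is partly broken and only the unmatched columns can be read.

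Section 6.3.2 makes multiple imputation primary without naming its predictors. Section 13 is blank, and the Table 4 shell in section 14.4 is laid out for hazard ratios, so no regression for the change in HbA1c is described.

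**The concern.** This is a non-randomised comparison of HbA1c change against a margin of 0.4. Two patients with the same last value, one rising steeply and one stable, look identical to a propensity score that holds only that value. Their histories may have influenced which drug was prescribed, and they may predict different next values. If history differs between arms at equal last value, the estimated difference carries that imbalance.

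The arms do differ before matching in how care is delivered: Appendix B gives 0.13 endocrinologist visits for glimepiride against 0.27 for liraglutide, and a standardised difference of -0.331 in pharmacy cost. This does not show that HbA1c history differs, but it makes the question reasonable.

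Earlier HbA1c values are also natural predictors of a missing later one. The price of having them, most of the remaining cohort, has already been paid.

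**Working it through.** **1. The plan's own figures.**
- Section 5.3: 13,962 / 19,231 = 72.6%, shown as 73%.
- Appendix B: (8.16 - 8.18) / sqrt((0.96² + 0.99²)/2) = -0.0205, shown as -0.021.
- Sections 8 and 10: SD 1.01, margin 0.4, 90% power, 110 per group. From n = 2·SD²·(z_a + z_b)²/margin², one-sided alpha 0.05 gives 109.2, so 110. The labelled two-sided 0.05 (one-sided 0.025) gives 133.98, so 134. The stated figure matches only the former. Both lie far below the 373 matched pairs.

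**2. Outcomes not observed** (section 7 censoring table, unmatched cohort).
- Liraglutide: 1 - 233/378 = 38.4%.
- Glimepiride: 1 - 2,029/3,092 = 34.4%.

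**3. Is precision the issue?** Applying these rates to 373 pairs leaves about 230 and 245 observed outcomes.
- SE = 1.01 × sqrt(1/230 + 1/245) = 0.0927.
- Power at one-sided 0.025 and true difference 0 = Φ(0.4/0.0927 - 1.96) = 0.991.

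Power is about 99% on observed outcomes alone, so the case rests on bias and imputation.

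**4. Bias from omitting the earlier values.** Assumptions, since the documents give neither quantity: three pre-entry values per patient, equal variances, and an arm difference of 0.2 points in the mean of the two earlier values at equal last value.

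*Equal correlation ρ between any two values.* The coefficient on the earlier mean, given the last value, is 2ρ/(1 + 2ρ). Bias = coefficient × 0.2.

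| ρ | Coefficient | Bias | Share of 0.4 |
|---|---|---|---|
| 0.3 | 0.375 | 0.075 | 19% |
| 0.5 | 0.500 | 0.100 | 25% |
| 0.7 | 0.583 | 0.117 | 29% |

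Scaling by the documented SDs (1.01/0.96) moves the ends to 0.079 and 0.123, or 20% and 31%.

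*First-order autoregressive.* The last value carries all the information; the coefficient and the bias are 0.

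*Between the two.* If the true level is autoregressive (0.6-0.9 per interval) and each reading has noise (reliability 0.7-0.9), the bias is 0.01-0.07, about 2-18% of the margin.

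**5. How many new terms?** Let B be the baseline (last) value, M the earlier mean and D the change from M to B. Then D = B - M exactly. With B in a linear model, M or D can be added but not both; the two choices give the same fit.

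**6. Likely cost in pairs.** Going from three covariates (section 8) to the full list (section 9) took the match from 376 to 373 pairs, a loss of 3.

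**The case against.** The strongest objection is that the effect may be zero. It needs a correlation structure and an arm difference that the documents do not supply, and what is visible gives no hint of imbalance: the last level and the number of test orders are nearly equal even before matching. Both arms also face the same 7-11% entry rule, so regression to the mean cancels unless histories differ, and it is not a separate harm. All of this stands. It limits the claim to a plausible confounder whose balance is unchecked. It does not remove the claim, because equal last values say nothing direct about earlier ones and the sponsor can measure their balance without looking at outcomes.

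Three stronger readings are tempting, and the documents do not support them.
- **A reader might infer that the plan excludes earlier values from the outcome and imputation models.** It is silent there, because neither model is specified. Only the baseline definition and the visible covariate table point to the last value alone.
- **A reader might infer that using the earlier values is free.** Matching, balance and final power have been run and carry review dates. With no distinct-date rule, three records could be same-day duplicates, so a usable history is not guaranteed for everyone. Section 6.2 sets a 180-day covariate window, and other antidiabetic drugs are excluded for 180 days only, so older values may reflect a different regimen.
- **A reader might infer that 34-38% of the matched cohort will be imputed.** Those rates come from the unmatched feasibility cohort and include as-treated censoring; the plan does not say that every censored patient is imputed.

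**Conclusion.** The point holds as a worthwhile improvement to the adjustment set and as a gap in specification. The plan secures repeated pre-entry HbA1c results at the cost of 73% of the patients then remaining, and where it specifies an HbA1c level it uses only the last.

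For an assumed 0.2-point arm difference in the earlier mean at equal last value, omission costs between 0 (first-order autoregressive) and about 0.08-0.12 (equal correlation 0.3-0.7; 19-29% of the margin). No correlation or earlier-value balance in the documents narrows that range, and the direction of any bias is unknown. The conclusion also relies on a partly broken Appendix B table in which no earlier HbA1c level can be seen. Section 13 is blank and the balance work used a dummy outcome, so on this document the addition can still be pre-specified before any comparative result.

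**What to change.** 1. Add one covariate to the propensity score beside baseline HbA1c: the mean of the HbA1c values in the 365-day window that precede the baseline value, taken on distinct dates. Do not also add the change from that mean.
2. State how same-day duplicates are handled, and report how many patients have no earlier distinct-date value.
3. Show the balance of the earlier mean in Table 1, before and after matching.
4. Name the imputation predictors, including the earlier mean and baseline HbA1c, and include both in any outcome regression.

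**Cost.** No new data source is needed, since the results are already used for inclusion 2.1. The match, balance and power steps must be re-run and re-reviewed, and a few pairs may be lost. This covariate needs its own 365-day window, and the report should note that values older than 180 days may have been measured on a different regimen.
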